#### 8) Procedures or Methods Involved

#### POLs:

Individuals must provide informed written consent to participate in the POL training. The training will cover contextual, etiologic and practical knowledge related to SAVAME syndemic and COVID-19 and its impact on the community; knowledge of and navigation through available SAVAME services; effective communication and messaging skills; and culturally appropriate screening, counseling, and referral/navigation techniques. Training will also cover resilience competencies (e.g. self-awareness, self-regulation, optimism, mental agility, strengths of character, and connection). POLs will be formally connected with service organizations via informative panel sessions with local service providers to facilitate referrals to these services. Finally, CRiSOL peers will be trained in rigorous and ethical data collection and documentation of activities; and professionalism and leadership skills. The training will use instruction, modeling, and extensive role play exercises to promote skills and confidence. In order to encourage attendance to the training program, POL's will receive transportation tokens for ten inperson training sessions at TPAC ([name]). We foresee a scenario in which some POLs might have to miss a training session, and we would like to have video recordings of the training sessions available to them to stay on track with the training to avoid any potential risk of loss of confidentiality, these videos will be edited by our team to remove any information that the participants might share, or any discussions unrelated to the training content.

At the beginning and end of each training session, subjects will complete a questionnaire to assess pre/post short term changes in SAVAME-related knowledge, attitudes, counseling skills, self-efficacy and behavioral intentions to influence and support others, as well as their individual resilience. These questionnaires will cover knowledge, attitudes, self-efficacy, resilience, and behavioral intentions to practice the skills covered during each session, while in the initial training phase (first 10 sessions). All of the questionnaires will be completed using iPads provided by the project. For the second year, the pre/post questionnaire will be about COVID-19 related knowledge, skills, and self-efficacy.

After 1 month of the implementation period (Community experience phase), the research team will conduct a semi-structured interview to gather opinions and overall satisfaction with the training, suggestions for amendments to the training in the future and their experience during the first month of community outreach. At the end of the 8-month implementation period (community experience phase), the research team will conduct semi-structured qualitative interviews with POLs, regardless of their continuation or level of activity. These interviews will

be conducted by trained project staff at TPAC offices. Questions for the exit interview will focus on the self-reported impact the training and application of CRISOL program had on POLs, including their assessment of the level, relevance, and quality of knowledge and skills acquired; impact on self-confidence, resilience, social capital, their role in the community, and future professional and personal plans. Interview guides will also cover challenges to serving as a POL, barriers and facilitators for their role, suggestions for ongoing support system, and ideas to maximize the impact of CRISOL on the community. This information will guide future improvements of the intervention.

POLs will document their activity in the community on the "POL Activity Log Survey" using iPads furnished with an offline Qualtrics® survey. POLs will log every interaction with community contacts and indicate the date, time, and place of the contact. POLs will also document their response to the issues discussed with the community contact which may include modeling of positive social norms, delivery of risk/harm reduction counseling, communication of health messages, linkage to resources, and navigation services to reduce SAVAME risk and impact. Collectively, we expect POLs will reach and register approximately 720 community contacts.

Project staff will also hold 16 bi-weekly recurring meetings (i.e. in person or via Zoom) with POLs after the training during the community contacts portion of the research study. Project staff will assess any additional support they can provide to POLs and track progress on the community contacts research. For the purposes of the intervention and to recruit individuals interested in being POLs and to increase awareness among community members about the CRISOL project, the project team will be creating a CRISOL Facebook, and Instagram accounts. This strategy has become a standard in today's community-based projects and an effective way to reach minority populations. For example, [name] from Temple University, a member of our research team, works with Latino populations on MSM issues using social media platforms (Twitter, Facebook, and Instagram) without any reported adverse events thus far. Creation of CRISOL social media accounts would also increase the perception of cohesiveness between the Latino-serving work that both Drexel and Temple Universities are engaging with. Recruitment flyers and photo updates of the POL intervention (uploaded after receiving consent from individuals in the photos) will be posted on social media accounts.

For the second year, after completion of first year intervention, POLs will be invited to participate in a second-year intervention. Those that accept to continue will undergo a COVID-19 16-hour training. Additionally, we will recruit new leaders to the project using a flyer. After which, they will continue with the community outreach phase for 9 months. POLs will document their activity in the community of this new phase on the "COVID Activity Log Survey". It is expected that each POL will connect with a minimum of 10 contacts each month. During the community outreach phase project staff will also hold 18 bi-weekly meeting (in person or via zoom) with the POLs.

#### Community contacts:

Post interaction with POLs, community members will complete a brief anonymous "Satisfaction Survey" based on their interaction with the POL, in addition to basic sociodemographic

characteristics. Community members will be provided with the informed consent script and must agree to participate before beginning the survey. The CRiSOL survey would be self-administered when the POLs and community contacts meet face-to-face, or administered by the POLs when interactions are made via phone or other media. The latter situation will be the case when social distancing measures are in place due to the coronavirus. The survey relies on Qualtrics®.

Note that by closing the survey, the answers of the individual cannot be accessed anymore except by the research team and no names or identifying information is included in the survey. A small incentive (i.e. a tote bag with the logo of the project) will be given to participants for their time when interactions are done face to face. This will not be possible when interactions are not face to face, such as during the coronavirus crisis.

For this second year, the study will be similar. Community members will complete an anonymous brief "satisfaction survey" after giving verbal consent (use of short consent version). Additionally, for this second year we are adding a new survey. POLs will invite community members to participate and collect phone numbers of the ones that agree. The research team will contact the community members that expressed interest, provide with a copy of the verbal consent and provide a link for them to take the survey. This survey will not collect any personal data. 300 community contacts will be invited to complete a follow-up survey 3 months after the completion of the first survey. The personal information needed to contact participants (i.e. phone number and first name) will be stored in a password-protected document.

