#### Community contacts:

As interventionists and data collectors, POLs will interact (i.e. face to face, social media, by phone) with community contacts within their own social networks during POL outreach. They will document the reach of the intervention using iPads provided by our project and equipped with the Qualtrics survey software offline application or using a link on their phones.

Every time they interact with a community contact as part of the CRiSOL intervention, they will fill out a brief questionnaire (i.e. "POL Activity Log Survey"). Post interaction with POL, POLs will go through a brief verbal consent process and ask community members to complete a brief anonymous 2-minute "Satisfaction Survey.", followed by basic demographic characteristics to understand the population they are reaching. For a clearer description of the process, see the study timeline in the next section. If the contact was not made face to face, the POL will ask the community member to complete the survey through an online anonymous survey.

Inclusion criteria for the community interaction is as follows:

• 18 or older

- Bilingual in English or Spanish
- The POL had a conversation with them or provided services to them as part of the CRISOL intervention.

We will use a shortened version of the consent form considering the information to be collected is not sensitive and consisting only of satisfaction items and demographics. Also, please, note that the surveys will not contain any contact information.

After completion of this survey, the POL will invite the community member to participate in a more in-depth 20-minute survey that will be managed by our staff. If the participant accepts, the POL will collect a phone/email so our staff can send the link for the survey. Additionally, participants will be invited to complete a follow-up survey 3 months after the first survey.

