#### Community contacts:

As described above, after graduation, POLs will document their activity in the community using iPads furnished with an offline Qualtrics® survey. POLs will log every community contact they complete and indicate the date, time, and place of the contact ("POL Activity Log Survey"). For each community contact, POLs will document their community contacts' responses to the issues identified, which may include modeling of positive social norms, delivery of risk/harm reduction counseling, communication of health messages, linkage to resources, and navigation services to reduce SAVAME risk and impact. POLs will offer the community contact to take a satisfaction survey. The first survey ("Satisfaction Survey") can be self-administered by the community member and is designed to collect data on basic sociodemographic characteristics (e.g. age, gender, sexual orientation, race/ethnicity, etc.) and their satisfaction with the services received from the POL.

Collectively, we expect POLs will reach and register approximately 720 community contacts. These data will serve to establish the level of reach, implementation (feasibility), and maintenance of the intervention in the community and provide important community-level baseline data to describe the population reached by the POLs.

These quantitative data will be analyzed as follows: Parametric (one-way repeated measures ANOVA) or non-parametric tests (Friedman's test, general estimated equations), depending on

the level of measurement and observed distribution of the information. Analysis will be performed using IBM® SPSS® 22.0 and Stata 14.

All surveys offered as part of data collection on the community contact section of this protocol will be collected with and stored in Qualtrics®.

For the second year, we expect to follow same procedures as prior year. Additionally, we will be inviting community members to participate in an additional survey that measures risk behaviors and protective factors for SAVAME and COVID-19, as well as sociodemographic characteristics. After 3 months, those that expressed interest and gave consent will be contacted to complete a follow-up survey. These surveys will be collected and stored using Qualtrics ®.

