#### 13) Risks to Subjects

A small reasonable risk to participants is their loss of confidentiality. All qualitative interviews for both POLs and community contacts will be conducted in a private space, inside of a large office building in Center City, Philadelphia (TPAC). Risks to privacy will be minimized through staff ethics training, layered data security and by restricting access of sensitive information to

staff members who have a specific need for the information. Risks will also be minimized through requesting an NIH Certificate of Confidentiality.

Though the semi-structured interview guide used to interview POLs after their experience with the program will focus on their experience with the training and with the work in the community, it is possible that POLs may discuss their own personal experiences or those of others. With this possibility, comes the risk that some information may cause an emotional reaction. However, participants will be made aware that they can refuse participation at any time or reschedule the interview. Refusing to participate or rescheduling will not be held against participants. They will also be told to not use names or specific identifying information during the interview, as the interview will be audio recorded.

As part of the CRiSOL training, all POLs will be trained in the ethical treatment of study subjects and subject data with special emphasis in maintaining confidentiality. POLs will offer community contacts the opportunity to answer a sets of questions about their experiences and satisfaction with their encounter with the POL and basic demographic characteristics.

For community contacts, there is no potential risk since the information ask would not be sensitive. But we will minimize the potential for psychological discomfort by informing the participants that they are not required to participate in the study, that they should only share information they feel comfortable sharing, they can refuse to answer any questions or withdraw from the study completely, and that there is no penalty for not participating. Participants will also be informed that their personal information will be de-identified. The POLs who have had the contact with the community contact will not have access to the survey results and will not be involved in data analysis.

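### Protocol Sections 5 and 8 give different modes for the satisfaction survey when contact is remote; under Section 8 the POL would take ratings of their own service

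*Protocol*

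**What the plan says.** Protocol Section 5 (Community contacts) lists face-to-face, social media and phone as the ways a POL may reach a contact. For any contact that was not face to face, it states that "the POL will ask the community member to complete the survey through an online anonymous survey".

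Protocol Section 8 (Community contacts) describes the same anonymous Satisfaction Survey. It is self-administered when the two meet in person, "or administered by the POLs when interactions are made via phone or other media". It adds: "The latter situation will be the case when social distancing measures are in place due to the coronavirus". The second year is described there as similar, with no further rule on mode.

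Protocol Section 10 (Community contacts) says the survey "can be self-administered by the community member" and that it covers basic demographics and "their satisfaction with the services received from the POL".

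Two safeguards are stated. Section 8 notes that "by closing the survey, the answers of the individual cannot be accessed anymore except by the research team". Section 13 says the POLs who made the contact "will not have access to the survey results and will not be involved in data analysis".

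**The concern.** The two rules cover the same contacts and the same questionnaire but assign different modes, so a POL with a remote contact cannot tell from the Protocol which to follow. If both are followed in practice, remote ratings will come from two different procedures.

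The choice matters because of what is being rated. A contact who answers through a link gives an opinion out of the POL's hearing. A contact who answers to the POL gives it to the person being judged, who belongs to the contact's own social network. Ratings given that way may be more favourable. The demographic items, which Section 10 says include sexual orientation, would also be given to someone the contact knows, on a survey described as anonymous.

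At stake is the credibility of the contacts' satisfaction data from remote interactions, which Section 8 expects while distancing is in force.

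**Working it through.** No arithmetic applies. The documents give no satisfaction scale, expected rating, mode effect, share of remote contacts or clustering by POL. The check is a comparison of the texts.

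1. **Same instrument.** Section 5 refers to the brief anonymous Satisfaction Survey given after the interaction. The Section 8 paragraph opens with that survey by name, and Section 28 (Consent Process) calls it the CRiSOL satisfaction survey. These are not two questionnaires.

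2. **Same contacts.** The Section 5 rule is triggered by any contact not made face to face, and that section names phone among the channels. The Section 8 rule is triggered by phone or other media. The sections therefore do not divide the work, for example phone to the POL and social media to the link.

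3. **Different modes.** Section 8 contrasts self-administration with administration by the POL, so the second cannot easily be read as merely sending a link.

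4. **Is it resolved elsewhere?**

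| Protocol section | What it adds | Does it settle the mode? |
|---|---|---|
| 2, IRB Review History | Data collection extended to online or phone | No; allows both, no rule for choosing |
| 4, Background | POLs survey their peers, including on satisfaction | No; remote mode not stated |
| 10, Data Management | Self-administration is possible | No |
| 19, Setting | Contacts may be by phone or online | No; survey mode not stated |
| 25, Privacy | All surveys run on Qualtrics | No; names the platform only |
| 28, Consent Process | POL gives the consent script before the survey | No |

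5. **What the POL learns.** Over the phone, a POL who administers the survey hears each answer. For other media the text does not say how answers are captured, but the contrast with self-administration makes it probable that the POL sees or enters them. The Section 8 safeguard starts when the survey is closed, so it does not cover the moment of answering. The Section 13 statement may mean stored results only. POL administration then does not break its wording, but it fits poorly with its intent.

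6. **What depends on these data.** Section 7 names acceptability among the things to be assessed but ties no instrument to it. Section 10 says the community contact data serve reach, implementation (feasibility) and maintenance. That satisfaction ratings inform acceptability is a plausible inference, not a statement in the plan. The SAP's outcomes (COVID-19 exposure risk, access to health care, SAVAME factors) come from the separate baseline and 3-month surveys. No satisfaction threshold or progression rule is given anywhere.

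**The case against.** The strongest reply is that POL data collection is a declared and reasoned choice. Section 4 says trained POLs will survey their peers, including on satisfaction, and calls this layering standard in peer-driven research. Section 5 calls POLs data collectors, and Section 8 trains them in rigorous and ethical data collection. This stands: having POLs collect data is not a mistake in the plan. It does not answer the inconsistency, because Section 5 itself sends remote contacts to an anonymous online survey.

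A second reply is that the consequence is speculative. This also stands in part. The bias may be zero, and face-to-face ratings are not free of it either: they follow the interaction directly, and a tote bag "will be given to participants for their time when interactions are done face to face".

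A third is that interviews with POLs and facilitators also gather satisfaction and barriers. They do, but they give the views of POLs and facilitators, not of contacts.

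A reader might go further and infer that recording the mode would let the analyst estimate or remove the bias by comparing modes. The documents do not support that. Between the two remote routes, contacts who cannot or do not use a link are self-selected. Between face-to-face and remote, the mode also moves with the distancing period and the gift.

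**Conclusion.** The inconsistency is certain: Sections 5 and 8 assign different modes to the same survey for the same remote contacts, and nothing reconciles them. The consequence is less certain. Under Section 8 the POL learns the rating of their own service as it is given (certain by phone, probable by other media), and ratings may be inflated by an amount that cannot be sized from the documents and may be nil.

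A reader might infer that the trial's efficacy results or its primary endpoint are compromised. The documents do not support this. No SAP outcome uses satisfaction, the link to acceptability is inferred, and the data are descriptive with no decision rule attached. A reader might also infer a breach of the Section 13 promise, but that wording can fairly be read as covering stored results only. Nor is there a basis for saying that the bias is larger or smaller than sampling error, since every input to such a comparison would have to be assumed.

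Priority: minor. The reason to act is that the problem is cheap to avoid at collection and hard to separate out afterwards.

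**What to change.** Bring Section 8 into line with Section 5: for contacts not made face to face, the POL sends the anonymous Qualtrics link through the channel already in use and does not take the answers.

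If POL administration is kept, limit it to a stated fallback for contacts who cannot use the link. Then:
- record the mode for every response;
- report fallback responses separately, as description only, and do not present the difference between modes as an estimate of bias;
- clarify in Section 13 that in this mode the POL learns the answers as they are given, although not afterwards.

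Call-backs by staff are a poor substitute. The survey is described as anonymous, and the phone or email details in Section 5 are collected for the longer staff-managed survey.

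The cost is a wording change in Section 8, a clarification in Section 13 and, if mode is not already captured, one survey field (the questionnaire is not in the documents). The downside is possibly fewer responses from contacts with limited internet access, by an unknown amount. The link reduces the pressure to please but does not remove it, since the POL still issues the invitation.

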## **Program Facilitators:**

After the training the research team will conduct a semi-structured interview with the facilitators to gather opinions and overall satisfaction with the training and suggestions for amendments to the training in future iterations. Due to COVID-19, interviews will be conducted over phone or via Zoom.

# 9) Data Banking

All data will be retained for at least three years after the completion of the research. Only individuals who are members of the research team and have been approved by the IRB will be allowed to access the data.

#### 10) Data Management

Only individuals who have been approved by the IRB will be allowed to access this data. All data files will be encrypted, and password protected with passwords known only to the principle investigator, co-investigators, and other authorized members of the research team. Additionally, the CRiSOL team has obtained a Certificate of Confidentiality from the NIH to protect program participants in this study. All digitized records will only be accessible from password-protected computers. Information containing participant information will be stored in password-protected documents, and participant identifiers will be used in place of names. All data recorded on paper will be kept in a locked drawer in a project office. The researcher who collected the paper

records will be responsible for transporting the data in a closed backpack or sealed folder from the intervention site to the project office. No paper records will include full participant name, sensitive information, or survey data. All other data will be retained for at least three years after the completion of the study except for contact information for community contacts.

